- a) At the end of the 12 weeks, the interventional arm will reach a clinically meaningful change in walking ability, as compared to controls, measured by a change in the 6-MWT at twelve-week, and 12 months; the minimal clinically important difference (MCID) is defined as +12m (7).

- b) At the end of the 12 weeks, $\geq 15\%$ interventional treatment arm participants will give up smoking or have significantly reduced their daily smoking compared to less than $\leq 10\%$ in the control arm.
- c) At the end of the 12 weeks, $\geq 50\%$ of interventional treatment arm participants will improve their medication adherence from pre- until post-intervention as compared to $< 30\%$ in the control arm.
- d) Healthcare cost will be reduced at 12 month follow-up in the intervention arm.

III. METHODOLOGY

We will implement a randomized controlled study of a 12-week lifestyle intervention for patients with peripheral arterial disease, delivered via the digital platform Sidekick Health. Participants will be recruited and randomized in a 1:1 manner to the digitally delivered intervention + standard of care or standard of care only. The standard of care group will receive an information leaflet on important lifestyle factors for PAD and smoking cessation and medical adherence will be encouraged by the health care provider. The interventional arm will receive a digital program delivered to their mobile phone alongside standard of care. Replicating a real-life scenario a personalized approach will be applied in the interventional arm, especially regarding smokers. Therefore, two pathways are possible in the interventional arm in this trial, one for smokers who want assistance in smoking cessation (PAD-SC) and another for non-smokers or those who smoke and do not desire to quit (PAD-Reg). Patients will be followed up at 12 weeks. We aim to do a separate follow-up at twelve months. The primary outcome will be a change in pain-free and maximal walking ability, measured by the 6-minute walking test. Secondary outcomes will include smoking status change (in PAD-SC group as compared to the control arm), medication adherence and lifestyle changes (increased physical activity, changes in self-assessed stress/energy/sleep quality levels), health-related quality of life, and a reduced need for hospitalization or revascularization due to PAD at 12 months of follow up.

Subject selection

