Individuals willing to participate and who provide written informed consent to the study will be further assessed and screened based on the inclusion and exclusion criteria presented in Table 1.

Table 1. Participant Criteria

Inclusion	Exclusion
Adults with confirmed PAD referred to a vascular surgery unit for evaluation and treatment, currently on best medical treatment and own/have access to a mobile smartphone	Critical limb ischemia, prior amputation, or other diseases/impairment that limit the walking ability and the 6-minute walk test's proper conduct
Stable PAD disease and limb symptoms during the last 3 months.	Cognitive impairment
PAD is the activity-limiting disease	Prior revascularization less than one year ago
Abnormal resting ankle-brachial index (≤ 0.90), falsely elevated above 1.3 or a 30% post-exercise ABI reduction.	A planned revascularization procedure during the upcoming 12 months (known at baseline)

Subject enrollment

Patients will be recruited by a clinic nurse or a medical doctor at participating centers (via telephone or during a scheduled in-person visit). Once agreed to participate and after signing informed consent, then the inclusion and exclusion criteria will be explored. Patients failing the screening process (do not meet the inclusion/exclusion criteria) may not participate in this study. Reasons for screen failure will be documented, but no other data will be collected. Participants who meet the criteria will be randomized to intervention or usual care in a 1:1 manner.

Based on a G*power analysis, the total number of patients in the two groups (intervention and control) will be 134, 67 in the intervention group and 67 in the control group, with an anticipated effect size of $f = 0.15$, $\alpha = 0.05$, power = 0.80 and correlations between time points (baseline and final timepoint) estimated at $r=0.25$. Foreseeing an attrition rate of 15%, we aim to recruit 155 patients to the trial.

Study procedures

All participants:

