After recruitment, measurements and data collections will occur at each clinic by a experienced clinic or research nurse, as shown in table 2 and further detailed under section VIII. Furthermore, a 6-minute walking test will be administered by a trained clinic nurse at baseline, after 12 weeks and for a separate follow-up at 12 months. The American Thoracic Society protocol for the 6-minute walking test, modified for patients with intermittent claudication (IC), will be used. The 6MWT has excellent test-retest reliability for patients with IC. (8, 9). A central computerized procedure will randomly assign participants to treatment arms, stratified for study site and smoking status.

Intervention:

Participants will be instructed to download the SKH mobile app, and they will receive an access code to activate the PAD lifestyle change program. After the first week of the program, participants who smoke will be offered to incorporate smoking cessation support into their PAD program. These changes are minor and not intended to divide the intervention group in two but instead personalize the experience. Personalization of the program is essential for engagement and to deliver the most meaningful impact on clinical outcomes. The program aims to empower positive lifestyle change by gamification, altruistic rewards, and engaging content with relevant tasks or missions to be completed. Beyond this, all patients in the interventional arm will also receive standard of care as defined below for the control arm.

Participants in the intervention group will also be asked to do a separate and virtually delivered 6-minute walking test to validate the digital in-app 6MWT.

Control:

All patients in the control arm will receive best medical treatment including start or optimization of secondary preventive pharmacotherapy, smoking cessation advise and advise on modifiable risk factors. The control arm will also receive an information leaflet about relevant lifestyle modifications for PAD. After baseline measurements and data collection, there will be no scheduled visits by a health care provider until week 12.

Table 2. Timing of Proposed Data Collection and Instruments Used

Data collection/Instruments	Baseline	Post-Intervention (after week 12)	12-month follow-up
All participants (intervention and control)			
Demographic and Clinical/Medical Baseline Information (e.g., tobacco use, other risk factors, and comorbidities)	Yes	Yes	Yes
6-Minute Walking Test	Yes	Yes	Yes

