Vascular Quality of Life Questionnaire (VascuQoL-6)	Yes	Yes	Yes
Morisky Medication Adherence Scale (MMAS-8)	Yes	Yes	Yes
Quality of life questionnaire – assessed by EQ5D5L	Yes	Yes	Yes
Assessment of health literacy (HLS-EU-Q16 Swedish version)	Yes	-	-
Carbon Monoxide breath monitor (smokers only)	Yes	Yes	Yes
Smoking Readiness to Quit Ladder (smokers only)	Yes	Yes	Yes
Daily frequency of cigarettes smoked (smokers only)	Yes	Yes	Yes
Intervention arm only			
In-app 6-minute walking test	Yes	Yes	Yes
Free-living physical activity (measured as total step count per day)	Yes (week 1)	Yes	-
In-app metrics (e.g. stress/sleep/energy level self-assessment)	Yes (week 1)	Yes	-

Measures – copies of questionnaires will be included in this protocol when finalized in section VIII below (Study Questionnaires)

IV. BIOSTATISTICAL ANALYSIS

Variables to be collected

Participants' demographic and background information, including age, gender, height, weight (and BMI), tobacco use, co-morbid medical or psychiatric conditions, and information on any current medical therapy they may or may not be receiving will be collected. All participants should be on the best medical PAD treatment available for them, and the control arm will receive an information leaflet about relevant lifestyle modifications for PAD. A 6MWT, questionnaires, and validated survey instruments (10) will be administered both pre-and post-intervention and 12 months from the start of the intervention.

Primary Outcomes (Intervention KPIs)

As far as possible, evaluation of endpoints will be done by evaluators blinded to the treatment assignment (PROBE design).

- Walking Ability: Change in patients objectively measured walking ability (measured by the 6-Minute Walk Distance Test) from pre- to post-intervention and 12 months.

Secondary Outcomes

- Smoking status: Change in patients' daily smoking patterns from pre to post-intervention and at twelve months. This will be based on information from the patient, supported by read-outs from the carbon monoxide breath monitor at baseline, 12 weeks and one year.
- Medication adherence improvement.
- Lifestyle behavioral changes (measured in-app):
 - Changes in free living physical activity, measured as total step count per day (from baseline to week 12)
 - Changes in self assessed stress levels, measured on an ordinal scale from 0-10 (from baseline to week 12)
 - Changes in self assessed energy levels, measured on an ordinal scale from 0-10 (from baseline to week 12)

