 - Changes in self assessed sleep quality, measured on an ordinal scale from 0-10 (from baseline to week 12)

- Disease-specific health-related quality of life.
- Increased readiness to quit smoking.
- Comparing outcomes to health literacy.
- Comparing healthcare costs between groups. Following completion of the long-term follow-up at 12 months for all patients, a separate cost-effectiveness analysis will be undertaken, based on the prospectively collected EQ5D-5L data and accumulated costs per patient as registered in the participating hospital's cost-per-patient databases. Quality Adjusted Life Years (QALYs) and Incremental Cost-Effectiveness Ratio (ICER) will be the main analyzed endpoints.

[figure not shown]
Retention and Engagement

- Program uptake (number of app downloads, how many participants/potential quitters registered (including gender and age)
- Length of program participation
- Program usage patterns (how often do people visit, how many tasks are performed, which tasks (videos, daily tasks, other) are used/accessed, etc.)
- Pre/post assessment of medication therapy (as registered medication taken)

End of study

The formal trial completion is when the recruited patients have completed the 12-week intervention, but an extended follow-up at twelve months from study start will also be arranged.

IPAD STUDY DESIGN

Statistical Methods

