Analyses will be performed according to the intention-to-treat principle and per-protocol analyses. Baseline characteristics and raw score questionnaire outcomes will be summarized as mean and SD for continuous measures and absolute numbers and percentages in each group. Changes in each outcome between baseline, post-intervention, and later a 12-month follow-up will be compared between and within the groups using t-tests or non-parametric statistical tests as appropriate. For the between-group differences, 95% Confidence Intervals will be reported. Correlations will be run to explore relationships between variables. For the primary outcome analyses, Ancovas or Mixed Anovas (repeated measures anovas) will be used, correcting for covariates that are significantly different between groups. The size of the change in HRQoL will be related to minimal important change values for the VascuQoL-6. It will be further assessed through effect size calculations (effect size=the difference in mean values between baseline and follow-up, divided by the SD at baseline). Cohen's criteria for interpreting effect sizes will be applied (small, 0.2–0.5; moderate, 0.5–0.8 and large, over 0.8). The a priori level for statistical significance will be set at a 2-sided $P < .05$.

V. RISKS AND DISCOMFORTS

We expect minimal to no risks and discomforts to be associated with this study. The lifestyle/behavioral change program is guideline-compliant for PAD patients and has

been reviewed by several medical doctors, behavioral scientists, and specialists in vascular surgery. Psychosocial risks will be minimal as well.

VI. POTENTIAL BENEFITS

Potential Benefits to Participating Individuals

The hope is that the intervention will increase participants' walking ability, reducing IC symptoms and prevent revascularization, empower participants to change their lifestyle and smoking patterns for the better, or that they will quit smoking altogether. Further, this intervention may also improve other patient-reported outcomes (e.g., reduce stress, improve sleep) without causing significant harm. Although the expected benefits are limited for patients that are allocated to usual care in the study, the enhanced follow-up at 12 weeks and 12 months may allow for a more careful evaluation and subsequent treatment of their condition following the end of study.

Potential Benefits to Society

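### The primary model is left open between ANCOVA and mixed ANOVA, with covariates picked by a significance test; one ANCOVA fixed in advance, with baseline 6MWD, site and smoking status, is a nearly free improvement

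*Combined protocol and SAP*

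**What the plan says.** Section IV, Statistical Methods, gives the primary analysis in one sentence: "Ancovas or Mixed Anovas (repeated measures anovas) will be used, correcting for covariates that are significantly different between groups". It gives no rule for choosing between the two models and no list of candidate covariates. The same paragraph says that changes in each outcome "will be compared between and within the groups using t-tests or non-parametric statistical tests as appropriate".

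Section IV, Primary Outcomes, defines the endpoint as "Change in patients objectively measured walking ability (measured by the 6-Minute Walk Distance Test) from pre- to post-intervention and 12 months". Section III, Study procedures, says "A central computerized procedure will randomly assign participants to treatment arms, stratified for study site and smoking status". Table 2 schedules the 6-minute walk test at baseline in both arms. No section names baseline 6MWD, site or smoking status as a covariate in the primary model.

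**The concern.** The natural reading of the covariate rule is a test of baseline differences between the arms. After randomisation, any such difference is chance. Whether a variable deserves adjustment depends on how well it predicts the outcome, and a test of imbalance says nothing about that. The variable most likely to predict follow-up 6MWD is baseline 6MWD, and the rule would usually leave it out. Site and smoking status are balanced by the stratification, so the rule would rarely admit them, although analysis should normally follow the stratification.

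The choice between ANCOVA and mixed ANOVA also matters. With two visits they are different estimators with different precision. At stake are precision in the primary comparison and a primary model that is known before the data are seen.

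**Working it through.** **Inputs.** From Section III, Subject enrollment: f = 0.15, two-sided alpha 0.05, power 0.80, r = 0.25 between baseline and the final time point, 134 patients (67 per arm), 155 recruited with 15% attrition. No SD is given. Values of r above 0.25 and unequal SDs are assumptions.

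**1. The plan's own figure.** For a two-group, two-visit repeated-measures interaction:
- Noncentrality = f² × N × 2/(1 − r) = 0.0225 × 134 × 2/0.75 = 8.04. With 1 and 132 degrees of freedom, power is 80.4%, and 134 is the smallest even N that reaches 80%.
- Three visits would give 110, and a direct ANCOVA calculation with f = 0.15 would give 352. The stated N therefore rests on the two-visit mixed ANOVA.
- With two visits this test is the t-test on change. The implied difference is 2 × √(8.04/134) = 0.490 SDs of change. The SD of change is √(2(1 − 0.25)) = √1.5 outcome SDs, so the difference is 0.490 × √1.5 = 0.60 SD.

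**2. Precision of the two models (equal SDs).** Residual variance is 2(1 − r) for change and 1 − r² for ANCOVA on baseline. The ratio of confidence interval widths is √(2/(1 + r)). At r = 0.25 the variances are 1.5 and 0.9375. In each row the effect is set so that the change score has 80.4% power with 67 per arm:

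| r | Difference (SD) | Change score / mixed ANOVA | ANCOVA on baseline | Change-score interval wider by |
|---|---|---|---|---|
| 0.25 (plan) | 0.60 | 80.4% | 94.5% | 26% |
| 0.5 (assumed) | 0.49 | 80.4% | 90.2% | 15% |
| 0.7 (assumed) | 0.38 | 80.4% | 86.3% | 8% |
| 0.8 (assumed) | 0.31 | 80.4% | 84.3% | 5% |

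At r = 0.25 and 0.60 SD, ANCOVA reaches 80% power with 84 completers, against 134. With 155 × 0.85 ≈ 132 completers, power is 79.8% for change and 94.2% for ANCOVA.

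**3. Unequal SDs.** Let k be the follow-up SD divided by the baseline SD, with the baseline SD set to 1. The variance of change is 1 + k² − 2rk, and that of ANCOVA is k²(1 − r²). The difference is (1 − rk)², which is never negative. At r = 0.25, the change-score interval is 44% wider at k = 0.8 and 9% wider at k = 1.5. At r = 0.8 and k = 1.25, both variances are 0.5625 and nothing is gained.

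**4. What the covariate rule admits.** A 5% test on a randomised baseline variable is significant in about 5% of trials. In simulations of 134 patients with stratified permuted blocks (assumed blocks of 4 or 8; 2, 3 or 8 sites), baseline 6MWD entered in 2.9% to 4.7% of trials. Site or smoking status entered in none of 35,000. The protocol does not give the block scheme, so rarely is the safe statement for those two.

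**5. If ANCOVA always contains baseline.** The same simulations assumed that strata explain 10% of the variance, and listed covariates 10% (r = 0.25) or 20% (r = 0.8). The rule with baseline always included had 94.0% power, against 95.6% for a fixed ANCOVA with baseline, site and smoking status (r = 0.25, 0.60 SD). At r = 0.8 and 0.3 SD it was 80.7% against 82.4%. The gain is 1.6 to 1.7 points.

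**6. Type I error.** Under the null the covariate rule rejected in 3.6% to 4.5% of simulated trials, whether combined with change or with baseline ANCOVA. If the model were chosen after seeing both results, the two test statistics correlate at √((1 + r)/2). Type I error would then be 7.9% at r = 0.25 and 6.5% at r = 0.8 (simulated 7.3% and 5.8%).

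**The case against.** The strongest reply is that an ANCOVA of a pre/post measure normally carries the baseline value, and that the endpoint is defined as a change from baseline. On that reading one of the two permitted models is already efficient and the gain is only 1 to 2 points. This stands as a possible reading, but the text does not say it, and the sample size follows the other model. On any reading the choice of model stays open and covariates are still selected by significance.

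Second, the large gain depends on r = 0.25. Section III itself says "The 6MWT has excellent test-retest reliability for patients with IC", which suggests a higher correlation and hence a smaller gain. This stands. Neither 94.5% power nor 84 completers should be promised.

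Third, Table 2 has three visits, so the mixed ANOVA may be meant for all visits and the ANCOVA for one. That is possible. The equivalence with a t-test on change is claimed only for the two-visit comparison on which N was based.

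A reader might infer more than the documents support:
- *The trial is underpowered.* It is not on this ground: the mixed ANOVA delivers the planned 80.4% on the plan's own inputs.
- *The covariate rule inflates type I error.* It does not; it was slightly conservative. Inflation needs a choice made after seeing both results, and nothing in the documents says that this is intended.
- *Disagreement between the two models is a second, separate harm.* At r = 0.25 and 0.60 SD they differed on significance in 15.7% of simulated trials with baseline as the only covariate. In 14.9 of those points only the ANCOVA was significant, which is mostly the power gap restated.

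**Conclusion.** The point holds as an improvement to the primary analysis that should be made. The covariate rule selects on chance imbalance, and no section fixes the model. For the two-visit comparison, ANCOVA on baseline 6MWD is never less precise than change or mixed ANOVA, apart from one degree of freedom.

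The size of the gain is conditional. It is about 14 points of power at the plan's r = 0.25 with equal SDs, about 4 points at an assumed r = 0.8, and nil at r = 0.8 with an SD ratio of 1.25. It is about 1 to 2 points if the plan's ANCOVA already includes baseline. The documents give no SD and no other r, so the gain cannot be narrowed further. Fixing the model also removes any chance of choosing it after the results are seen.

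**What to change.** Replace the sentence in Section IV, Statistical Methods, with:

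*The primary analysis compares 6MWD at the primary time point between the randomised arms by ANCOVA, adjusted for baseline 6MWD, study site and smoking status. No covariate will be chosen by a significance test.*

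State that t-tests on change and repeated-measures ANOVA are supportive. Set a rule in advance for pooling very small sites.

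The cost is wording and a few degrees of freedom for site. No patient, visit or measurement is added: baseline 6MWD is in Table 2, and site and smoking status are needed for the randomisation.

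Which time point (12 weeks or 12 months) and which distance (pain-free or maximal) is primary is a separate matter for the sponsor to confirm. The wording above works with either answer, provided that the baseline value of the chosen distance is the covariate.

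### Under a stated intention-to-treat principle, the plan lets the primary 6MWT analysis be a classical repeated-measures ANOVA, which keeps only participants seen at every modelled visit; a likelihood-based mixed model should replace it

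*Combined protocol and SAP*

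**What the plan says.** The Statistical Methods part of section IV sets the principle: "Analyses will be performed according to the intention-to-treat principle and per-protocol analyses". For the primary outcome it says that "Ancovas or Mixed Anovas (repeated measures anovas) will be used", with adjustment for those covariates on which the arms turn out to differ significantly. It does not say which of the two methods applies, which visits enter, who belongs to the intention-to-treat set, or what happens when a 6MWT is missing. No imputation, likelihood-based model or missing-data sensitivity analysis appears anywhere in the document.

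On time points the document points two ways.

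- **Towards three visits.** The Primary Outcomes list defines the change in walking ability as "from pre- to post-intervention and 12 months". Hypothesis (a) also names both follow-up times, and Table 2 schedules the 6MWT at baseline, week 12 and month 12.
- **Towards two visits.** The Methodology section says "We aim to do a separate follow-up at twelve months", and End of study says "The formal trial completion is when the recruited patients have completed the 12-week intervention". The sample size under Subject enrollment uses a correlation between baseline and one final time point.

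Attrition is handled only through recruitment: "Foreseeing an attrition rate of 15%, we aim to recruit 155 patients to the trial".

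**The concern.** A classical mixed ANOVA needs a complete row for each participant, so anyone missing one modelled visit is deleted. Without a missing-data method, choosing this option means that the analysis labelled intention-to-treat covers complete cases only.

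Two things are at stake. The first is efficiency. If all three visits are modelled, week-12 measurements already collected are thrown away because a later visit was missed. Even with two visits, testing change by ANOVA uses the baseline value less efficiently than adjusting for it. The second is bias. In an open-label trial of an app, those who stop attending may be those who gained least. If so, the remaining complete cases flatter the app arm. The unresolved choice between two methods also allows the model to be picked after the data are seen.

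**Working it through.** **Inputs from the plan (Subject enrollment).** f = 0.15, alpha = 0.05, power 0.80, r = 0.25, N = 134 (67 per arm), attrition 15%, 155 recruited. Statistical Methods gives the test as two-sided.

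**Step 1: reproduce the plan's figure.** For the group-by-time interaction with two groups and m visits, the noncentrality is lambda = f² × N × m / (1 − r), on m − 1 and (N − 2)(m − 1) degrees of freedom.

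- m = 2, N = 134: lambda = 0.0225 × 134 × 2 / 0.75 = 8.04, power 0.804. N = 132 gives 0.798. So 134 reproduces exactly.
- m = 3 would need only N = 110 (power 0.806). The stated size therefore belongs to a two-visit model.
- Recruitment: 134 × 1.15 = 154.1, rounded up to 155.

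**Step 2: the plan's own attrition.** 155 × 0.85 = 131.75. About 23 of 155 randomised participants would have no final 6MWT. They would leave either a two-visit mixed ANOVA or an ANCOVA on observed data. Power of the change-score test is 0.795 at 131 and 0.798 at 132.

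**Step 3: if month 12 enters the ANOVA.** The document gives no separate month-12 loss, so a range is assumed for week-12 completers who miss month 12. Power is for the week-12 change contrast among those left.

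| Assumed further loss | Complete cases | Power |
|---|---|---|
| none | 131-132 | 0.795-0.798 |
| 5% | 125 | 0.776 |
| 10% | 118-119 | 0.751-0.755 |
| 15% | 112 | 0.729 |

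At 15%, for example, lambda = 0.0225 × 112 × 2 / 0.75 = 6.72.

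**Step 4: baseline adjustment.** In a two-by-two interaction, f = 0.15 means a difference in change of 4 × 0.15 = 0.60 SD. With equal variances, the variance factor is 2(1 − 0.25) = 1.5 for a change score and 1 − 0.25² = 0.9375 after baseline adjustment. At N = 134 the adjusted noncentrality is 0.60² × (134/4) / 0.9375 = 12.86, giving power of about 0.94, against 0.80 for the change test. At N = 118 and 112 the adjusted power is about 0.92 and 0.90.

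**Step 5: possible bias (simulation under assumed dropout).** Assumptions: 77 per arm; correlation 0.25 with baseline and 0.6 between follow-ups; random 15% loss at week 12; month-12 loss in the app arm of 25% if the week-12 value is below the baseline mean and 5% otherwise; 12.5% in controls.

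- With a true week-12 effect of 0.60 SD, the three-visit complete-case estimate was 0.65 to 0.67 SD. With no true effect it was about +0.07 SD.
- ANCOVA on all week-12 values was essentially unbiased.
- If the 25%/5% rule acts on the week-12 visit itself, so that the value is never seen, ANCOVA on observed data is also biased: about +0.07 SD with a true effect of 0.60 and +0.09 SD with none.

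**The case against.** The strongest reply is that the plan may never run the analysis described in Step 3. A reader might infer from the outcome list that an ANOVA over all three visits is specified. It is not. The Statistical Methods text names no visits, the sample size fits two, formal completion is at week 12, and the later comparison is staged: "Changes in each outcome between baseline, post-intervention, and later a 12-month follow-up will be compared between and within the groups". In a week-12 model, a missed month-12 visit removes no one. This stands, and it makes the three-visit loss conditional.

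A reader might also infer that the named method flatly contradicts intention-to-treat. That goes too far. ANCOVA is the first-named option and would keep everyone with a week-12 value, imputation is not excluded, and the principle can be read as analysis by randomised arm. The conflict is the default result of one permitted option, and ANCOVA on observed data shares part of it.

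The figures invite a third overreading. The further month-12 loss and the response-related dropout rule are assumptions, and nothing in the document links dropout to response. The 0.73-0.75 applies to the change-score test; baseline-adjusted ANCOVA keeps power of about 0.90 or more at the same numbers.

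Finally, a likelihood model is not a complete cure. It does not remove bias from response-related loss before week 12. If only baseline and week 12 are available, it uses the same information as ANCOVA on observed data.

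What the reply leaves untouched is that the plan permits a method that deletes incomplete participants and uses the baseline inefficiently, expects 15% attrition, and gives no missing-data method.

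**Conclusion.** The point holds in a limited form. As written, the plan allows a primary analysis that would be complete-case by default under an intention-to-treat label. On the plan's own figures, about 23 of 155 participants would be omitted.

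The further loss arises only if month 12 is put into the ANOVA. Then, assuming another 10-15% miss that visit, power of the change-score test falls from about 0.80 to 0.73-0.75. The estimate may be biased, by about 0.05 to 0.07 SD in the simulated example with a true effect of 0.60 SD, if that loss depends on response. This shows what could happen and is not evidence that it will.

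Independently of any dropout assumption, baseline adjustment at r = 0.25 gives power of about 0.94 at N = 134, against 0.80 for the change-based ANOVA. The change should be made before analysis; the point does not call the design or the recruitment target into question.

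**What to change.** Remove the mixed-ANOVA option and name one primary analysis: a likelihood-based linear mixed model for repeated measures, using all observed 6MWT values from all randomised participants in their allocated arm.

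- **Terms:** arm, visit, arm-by-visit interaction, baseline 6MWT distance, and the two stratification factors given under Study procedures (site and smoking status). These replace covariates chosen because they differ significantly between groups.
- **Primary contrast:** the difference between arms at week 12.
- **Acceptable equivalent:** a week-12 ANCOVA with the same covariates and multiple imputation.
- **Sensitivity:** because either version relies on data missing at random, add one prespecified analysis for data missing not at random, such as reference-based imputation for app-arm dropouts.
- **Definitions:** state who is in the intention-to-treat set, and label the per-protocol analysis as supportive.

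The cost is SAP wording, slightly more programming and an explicit reliance on missing at random. No extra participants, visits or data are needed.

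### The HRQoL effect size has no control-arm term and is not labelled descriptive, so a change shared by both arms can earn a Cohen label with no treatment effect

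*Combined protocol and SAP*

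**What the plan says.** All the relevant text is in section IV, under Statistical Methods, unless noted.

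- **Tests.** Changes in each outcome "will be compared between and within the groups using t-tests or non-parametric statistical tests as appropriate". The significance level is two-sided 0.05.
- **Between-arm estimates.** "For the between-group differences, 95% Confidence Intervals will be reported".
- **Model.** "For the primary outcome analyses, Ancovas or Mixed Anovas (repeated measures anovas) will be used". No model is named for secondary outcomes.
- **Clinical importance of HRQoL.** "The size of the change in HRQoL will be related to minimal important change values for the VascuQoL-6". No value is given, and the text does not say whether the benchmark is set against each arm's change or the difference between arms.
- **Size of the HRQoL change.** "effect size=the difference in mean values between baseline and follow-up, divided by the SD at baseline", after which "Cohen's criteria for interpreting effect sizes will be applied (small, 0.2–0.5; moderate, 0.5–0.8 and large, over 0.8").
- **Status.** "Disease-specific health-related quality of life" is listed under Secondary Outcomes. Improved quality of life is also part of the specific aim in section II.

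No sentence calls the effect size or the within-group tests descriptive, and none says that the between-group difference governs the HRQoL conclusion.

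**The concern.** The effect-size formula uses a baseline mean, a follow-up mean and a baseline SD. Whether it is applied to each arm or to both arms pooled, it does not contrast app with control. It therefore takes in everything that moves patients between visits: natural course, regression to the mean, and the standard care given to both arms. That care is active. Under Study procedures (section III), controls have secondary preventive drug treatment started or optimised, receive smoking and risk-factor advice, and are given a leaflet. Some improvement in controls is plausible.

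What is at stake is how the HRQoL result will be read. A report that follows the plan to the letter could state a moderate effect in the app arm next to a null between-group comparison, with nothing in the plan to say which one answers the trial's question. Within-group P values add to this, because significance in one arm and not in the other looks like a treatment effect and is not a comparison of the arms.

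**Working it through.** **Plan's own figure.** The documents give no figure for the HRQoL effect size. The figure that can be checked is the sample size, which also supplies the number per arm. For a two-group, two-time-point within-between interaction with f = 0.15 and r = 0.25 (section III, Subject enrollment), the noncentrality is λ = N·f²·m/(1−r) = 134 × 0.0225 × 2 / 0.75 = 8.04. This gives power 0.804, so 134 (67 per arm) reproduces.

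**Inputs for the check.**
- From the documents: n = 67 per arm and two-sided α = 0.05. The value r = 0.25 is also theirs, but it is stated for the sample-size calculation, not for VascuQoL-6.
- Assumed: equal true improvement in both arms of 0.3 or 0.5 baseline SD, equal SDs at both visits, and r = 0.5 and 0.7 as alternatives. The documents give no VascuQoL-6 SD, expected change or correlation.

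**Effect size under a shared change.** The plan's formula has expectation 0.3 or 0.5 in the app arm. The between-arm effect size is 0.3 − 0.3 = 0 or 0.5 − 0.5 = 0.

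**Within-arm test.** In baseline SD units, the SD of change is √(2(1−r)): 1.225, 1.000 and 0.775 for the three correlations. The standardised change is dz = shared change / SD of change. The power p of a paired t-test comes from a noncentral t with noncentrality dz·√67. The arms are independent, so P(app significant, control not) = p(1−p). At 0.3 SD:
- r = 0.25: 0.506 × 0.494 = 0.250
- r = 0.5: 0.677 × 0.323 = 0.219
- r = 0.7: 0.878 × 0.122 = 0.107

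The last three columns below come from 20,000 simulated trials per row. The true treatment effect is zero in every row.

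| Shared change (SD) | r | dz | App arm P < 0.05 | App significant, control not | App-arm effect size ≥ 0.2 | App-arm effect size ≥ 0.5 | Between-group test P < 0.05 |
|---|---|---|---|---|---|---|---|
| 0.3 | 0.25 | 0.245 | 51% | 25% | 75% | 10% | 4.93% |
| 0.3 | 0.5 | 0.300 | 68% | 22% | 80% | 7% | 5.05% |
| 0.3 | 0.7 | 0.387 | 88% | 11% | 85% | 3% | 4.90% |
| 0.5 | 0.25 | 0.408 | 91% | 8% | 98% | 50% | 4.93% |
| 0.5 | 0.5 | 0.500 | 98% | 2% | 99% | 50% | 5.07% |
| 0.5 | 0.7 | 0.645 | >99% | 0.1% | >99% | 51% | 4.92% |

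**Reading the table.** The two problems arise at different sizes of shared change. The one-arm-only pattern peaks at 25%, the maximum of p(1−p), when within-arm power is near one half; it fades as the shared change grows, because both arms then become significant. The Cohen label becomes more misleading as the shared change grows. At 0.5 SD the expected value is on the threshold for moderate, so about half of trials get that label or higher and nearly all get at least small.

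**The case against.** The strongest reply is that the plan already contains the right comparison. Changes in each outcome, HRQoL included, are to be tested between groups with 95% CIs, and that test holds its level. This stands in full.

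A reader might infer that the plan will claim an HRQoL benefit because the app arm is significant and the control arm is not, or that the before-after effect size is its sole measure of benefit. The documents support neither. The text speaks of the size of the change, not of benefit. No sentence ties a treatment claim to within-arm significance, and the walking, smoking and adherence hypotheses in section II are framed against controls. For the same reason 11% to 25% must not be read as a false-claim rate; it would become one only if authors set the planned between-group result aside. The range also depends on the assumed shared change and falls to 8% or less at 0.5 SD.

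It can further be said that if the effect size is reported for both arms, two similar labels would show the reader that nothing separates them. That helps only if both are reported and compared, which the plan does not require.

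Finally, within-group analysis cannot simply be struck out. Table 2 lists step count and the in-app stress, sleep and energy ratings under the intervention arm only, so no between-arm comparison is possible for them.

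What survives is narrower. The Cohen label attaches to a quantity with no control contrast, the minimal important change (MIC) has no stated comparison, and nothing ranks these below the between-group difference.

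**Conclusion.** The point holds as a fault in how HRQoL is sized and interpreted. It is not a fault in the planned between-group test, which is valid and stays at about 5% two-sided (about 2.5% in favour of the app) when the arms do not differ.

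That the formula has no control-arm term follows from the text alone and needs no assumption. The percentages rest on the assumed shared changes of 0.3 and 0.5 baseline SD, on correlations of 0.25 to 0.7, and on 67 analysed per arm. Other values would move them, but a shared change would still enter the effect size in full.

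HRQoL is a secondary outcome. The primary walking-test analysis and the sample size are unaffected. The change is worth making because it replaces a stated but uninformative quantity with one that measures what the app adds.

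**What to change.** In Statistical Methods:

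1. Define the VascuQoL-6 effect size as the baseline-adjusted (ANCOVA) between-arm difference at week 12 and at month 12, divided by the pooled baseline SD, with a 95% CI. Apply any Cohen label to this quantity.
2. Relate that difference, or the between-arm difference in the proportion of patients reaching the MIC, to the MIC. State which is used and the MIC value.
3. State that the HRQoL conclusion rests on this between-arm result.
4. For outcomes measured in both arms, report within-arm changes and effect sizes as descriptive, with CIs and without P values.
5. Keep within-arm analysis for the in-app outcomes collected only in the intervention arm (steps, stress, energy, sleep), and label it as uncontrolled.

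The cost is wording only: no new data, visits or patients. The downside is that reported HRQoL effect sizes may look smaller than before-after ones.
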